### 7.6.4 Subgroup Analysis

The primary and key secondary efficacy endpoint will be analysed using the ITT population by the following subgroups:

- Charlson Comorbidity index (as derived using the eCRF data): 0 1' or > 1'
- Geographical Region: Europe or Rest of the World
- Pre-baseline Barthel index:  $\geq 90'$  or  $\leq 90'$
- Patients included before and after amendment: 'Protocol v.6 or before' or 'Protocol v.7'

The same covariates used for the primary efficacy endpoint analysis will be used for the subgroup analyses except that for the Charlson Comorbidity index subgroup analysis, the randomisation stratum of Charlson Comorbidity index will not be included as a covariate; for the Geographical Region subgroup analysis, the randomisation stratum of Geographical Region will not be included as a covariate; and for the pre-baseline Barthel index subgroup analysis, the randomisation stratum of pre-baseline Barthel index will not be included as a covariate.

Additionally, the primary efficacy endpoint will be analysed by the following subgroups:

- Sex: female or male
- Age at study entry: '18 to 39', '40 to 64' or ' $\geq$  65 years'
- Race: Asian, black, white or other
- Ethnic group: 'Hispanic or Latino' or 'Not Hispanic or Latino'

- Site location: each study site with more than 1/6 out of the randomised patients (ie, >33 randomised patients for the futility analysis and >101 randomised patients for the final analysis) will be considered as a group and the remaining study sites, ie, those study sites with less than 1/6 out of the randomised patients will be pooled together as a one single group.
- Use of antiviral therapies or immunomodulatory drugs through the study: Yes or No
- Previous COVID-19 vaccination status: 'Fully vaccinated', 'Non-fully vaccinated', 'No vaccinated', or 'Fully vaccinated + Non-fully vaccinated'
- Anti-SARS-CoV-2 IgG at Day 1: 'Non-positive' or 'Positive'
- Pre-randomisation dexamethasone: Yes or No
- Total duration of corticoid therapy: `< 9 days', `[9 11] days' or `> 11 days'
- Total cumulative dose of corticoid therapy (dexamethasone or equivalent): `≤ 60 mg' or `> 60 mg'
- SARS-CoV-2 viral load (log10 copies/mL) at Day 1 before study drug administration: '< 4', `[4 - 7]' or `> 7'
- Time between onset date of COVID-19 symptoms and initiation of study treatment: `≤ 5 days', `6 - 10 days' or `> 10 days'
- Body mass index (kg/m^2) at Screening: < 30 or  $\geq$  30 (Obesity)
- Hypertension at Screening, defined as Hypertension (Standardised MedDRA Query [SMQ]) in the Medical History form: Yes or No
- Individual co-morbidities included in the Charlson Index: myocardial infarction (Yes or No), congestive heart failure (Yes or No), peripheral vascular disease (Yes or No), cerebrovascular disease (Yes or No), dementia (Yes or No), chronic obstructive pulmonary disease (Yes or No), connective tissue disease (Yes or No), peptic ulcer disease (Yes or No), liver disease ('None', 'Mild' or 'Moderate or Severe'), diabetes mellitus ('None or diet controlled', 'Uncomplicated' or 'End-organ damage'), hemiplegia (Yes or No), moderate or severe chronic kidney disease (Yes or No), solid tumor ('None', 'Localized' or 'Metastatic'), leukemia (Yes or No), lymphoma (Yes or No) or AIDS (Yes or No).
- ISARIC-4C mortality score: Low (0 3), Intermediate (4 8), High (9 14) or Very high (≥ 15)
- ISARIC-4C deterioration probability (%): `≤ 25', `(25 50]', or `> 50'
- Lactate dehydrogenase (LDH) at Baseline: ≤ ULN or > ULN

- CRP (mg/L) at Baseline: ≤ 100 or > 100
- D-dimer at Baseline: ≤ ULN or > ULN
- Ferritin at Baseline: ≤ ULN or > ULN
- Creatinine at Baseline: ≤ ULN or > ULN
- IL-6 at Baseline: ≤ Median or > Median value (at the analysis time cutoff may be updated based on distribution values if needed)
- IL-10 at Baseline: ≤ Median or > Median value (at the analysis time cutoff may be updated based on distribution values if needed)
- Lymphocytes count decreased at Baseline: 'Grade 0' or 'Grade  $\geq 1'$
- Neutrophils/lymphocytes ratio at Baseline:  $< 6 \text{ or } \ge 6$
- SARS-CoV-2 variant: Alpha, Beta, Gamma, Delta, Eta, Iota, Kappa, Lambda, Mu, or any potential new variant

The same covariates used for the primary efficacy endpoint analysis will be used for the subgroup analyses.

For ISARIC-4C mortality score and deterioration probability calculation:

- A Glasgow coma scale score of 15 is assumed for all the patients.
- Urea (mmol/L) will be calculated as blood urea nitrogen (mmol/L) \* 60 / 28.

Forest plots of the hazard ratios, and the 95% CI for the comparison of each dose of plitidepsin versus control arm will be presented by endpoint for all subgroups using the ITT population.

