#### Table 14.2.3.2.2 Post-hoc Analysis: Total Duration of Advanced Oxygen Support - All Patients Except Those from Site ES40 (Full Analysis Set)

The below tables are a repeat of table 14.2.3.9.1:

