#### Statistical Analysis Plan Addendum and TFL Mock Shells Fortrea Study: 000000213894 Protocol Reference: APL-D-003-20

#### Programming notes (not part of the figure):

Type of figure	Forest Plot					
Figure Template ID Treatment display details	FG006 Display 2 tro	eatment groups per page	e. Plitidepsin 2.5mg vs	Control Arm on page 1 and Pl	itidepsin 1.5mg vs C	ontrol Arm on
X-axis label	< ( < (	Control Arm Better Control Arm Better	Plitidepsin 2.5mg Be Plitidepsin 1.5mg Be	tter> on page 1. tter> on page 2.		
X-axis Scale	0.33; 0.5; 0.	66; 1; 1.5; 2; 3.				
Y-axis label	Nil.					
Y-axis Scale	Major tick: 1 Display 2 tro	Nil>>, Minor tick: Nil. eatment groups per page	·.			
	Subgroup	Plitidepsin 2.5mg N	Control Arm N	HR [b] (95% CI)	Hazard Ratio	(on page 1)
Legend	Subgroup	Plitidepsin 1.5mg N	Control Arm N	HR [b] (95% CI)	Hazard Ratio	(on page 2)
Legend position	Тор					
Annotations Other notes	Include refer Display sub	rence line groups as following:				
	Al Cl Ga Pr Pa Se	ll patients narlson Comorbidity Inc 0 - 1 > 1 eographical Region Europe Rest of the World e-baseline Barthel index ≥ 90 < 90 stients included before a Protocol v.6 or befo Protocol v.7 x Female Male	lex c nd after amendment re			

Statistical Analysis Plan Addendum and TFL Mock Shells Fortrea Study: 000000213894 Protocol Reference: APL-D-003-20

> Age at study entry (years) 18 to 39 40 to 64  $\geq 65$ Race Asian Black White Other Ethnic group Hispanic or Latino Not Hispanic or Latino Site location: each study site with more than 1/6 out of the randomised patients (i.e. >33 randomised patients for the futility analysis and >101 randomised patients for the final analysis) will be considered as a group and the remaining study sites, i.e. those study sites with less than 1/6 out of the randomised patients will be pooled together as a one single group Site XXX Site XXX Other Sites Use of antiviral therapies or immunomodulatory drugs through the study Yes No Previous COVID-19 vaccination status Fully vaccinated Non-fully vaccinated No vaccinated Fully vaccinated + Non-fully vaccinated Anti-SARS-CoV-2 IgG Day 1 Non-positive Positive Pre-randomisation dexamethasone Yes No Total duration of corticoid therapy  $\leq 9$  days [9 11] days > 11 daysTotal cumulative dose of corticoid therapy (dexamethasone or equivalent) ≤ 60 mg

Final, Version 2.0, 12SEP2023

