## 2.3 Sample Size and Power

A total sample size of 609 patients (203 in each arm) with 530 events necessary for the analysis of the primary endpoint has been calculated based on a 1-sided type I error rate of 1.25% ( $\alpha = 0.0125$ ) with at least 80% power ( $\beta = 0.2$ ) to detect target hazard ratio (HR) of 1.4 in the time to sustained withdrawal of supplementary oxygen, which means a decrease in the median time to the event from 8 days (control arm) to 5.7 days (plitidepsin). This sample size is adjusted for the multiple comparisons of each plitidepsin arm with control group by a Bonferroni adjustment, although other advanced methods for correction of multiplicity will be used for the main analysis that will increase the power of the tests. At the final analysis, if HR is 1.27 or greater, in favour of any plitidepsin arm, (equivalent to a decrease in the median time to sustained withdrawal of supplementary oxygen of 1.7 days or greater), then it is expected that the null hypothesis (ie, HR  $\leq$ 1) will be rejected.

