# 8. Changes in Planned Analysis

Despite wording in Protocol that WHO score 0 requires a test with RNA undetected (which would be achieved with a PCR or similar test), as scarce cases have been reported, Pharma Mar is accepting negative antigen tests (which is a protein detection test, and not RNA detection test) qualifying for score of 0.

Recruitment was stopped due to slow recruitment before reaching the 33% of events by Pharma Mar decision and futility analysis was cancelled.

An exploratory analysis of the comparison of the primary efficacy endpoint between each dose of plitidepsin versus control arm receiving and not receiving the antiviral control arm, ie, the regulatory-approved antiviral for those patients randomised to the control arm (remdesivir or favipiravir), will be performed.

CONFIDENTIAL

An exploratory analysis of the prior primary efficacy endpoint based on protocol amendment v6 will be performed at the final analysis time due to some regulatory agencies request.

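### The site-location rule contradicts itself: its final-analysis count of more than 101 is one sixth of the planned 609 patients and was not updated after recruitment stopped early

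*SAP*

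**What the plan says.** SAP section 7.6.4 lists site location among the subgroups for the primary endpoint. The criterion is a fraction, "each study site with more than 1/6 out of the randomised patients", and sites below one sixth are pooled into a single group. Between these two statements stands a parenthesis with counts: "ie, >33 randomised patients for the futility analysis and >101 randomised patients for the final analysis". The same counts appear in section 7.7.7 (safety subgroups), in the version 4.0 shell for Figure 14.2.1.2, and in the addendum's shell for Figure 14.2.1.2.1, dated 12 September 2023: "i.e. >33 randomised patients for the futility analysis and >101 randomised patients for the final analysis".

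Section 2.3 gives the planned size: "A total sample size of 609 patients (203 in each arm) with 530 events necessary for the analysis of the primary endpoint". Section 8 reports what happened: "Recruitment was stopped due to slow recruitment before reaching the 33% of events". It adds that the futility analysis was cancelled.

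The addendum also contains a series of tables for Site ES40 alone and for everyone else, for example "Total Duration of Advanced Oxygen Support - All Patients Except Those from Site ES40". These cover demographics, baseline characteristics, medical history, prior medication, symptoms, duration of advanced oxygen support, high-flow oxygen, non-invasive ventilation, invasive ventilation or ECMO, and corticoid therapy.

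**The concern.** The fraction and the count were two ways of saying the same thing at 609 patients. Once recruitment stopped far short of that, they became different instructions. The smaller count, more than 33, belongs to an analysis that was cancelled, so the only count left for the final analysis is the one built on the planned size. A programmer who follows it would pool sites that the rule's own fraction says must be shown separately.

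What is at stake is the display of site heterogeneity. The trial is open-label, and both oxygen withdrawal and discharge depend partly on decisions by local staff, so a reader will want to see whether large sites behave differently. The grouping feeds the primary-endpoint forest plot, the safety subgroup table and, through section 7.6.5, the site covariate in the multivariate Cox models.

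The leftover was overlooked on two occasions. SAP version 4.0 was issued partly to record the cancelled futility analysis. The addendum, written after database lock, reworked this same forest plot (it removes three subgroups and adds an IL-10 cut at 3.8 ng/L) but kept the counts.

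**Working it through.** **Inputs.** Planned size 609 patients and 530 events (section 2.3). Futility trigger 33% of events, given as 175 (section 7.8). Rule: more than N/6 (section 7.6.4). Recruitment stopped before the trigger (section 8). Actual N: not stated.

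**Reproducing the plan's counts.**
- Final analysis: 609/6 = 101.5, so a site needs at least 102, which is more than 101.
- Futility analysis: 0.33 × 609 = 201; 201/6 = 33.5, so at least 34, which is more than 33.

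Both counts are N/6 at the planned sizes. Rounded down, N/6 equals 101 only for N from 606 to 611.

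**Could the final N still be about 609?** At most 174 events had occurred when recruitment stopped. With 606 patients the event share would be 174/606 = 29%, against a planned 530/609 = 87%. The bootstrap in section 7.6.1, which resamples up to 203 per arm because recruitment was stopped, also shows that the planned size was not reached.

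**Size of the discrepancy.** Assume recruitment stopped just short of the trigger, with 174 events, and let the event share vary. N = 174/share:

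| Event share (assumed) | N | N/6 | 102 as share of N |
|---|---|---|---|
| 100% | 174 | 29.0 | 59% |
| 95% | 183 | 30.5 | 56% |
| 87% (as planned) | 200 | 33.3 | 51% |
| 80% | 218 | 36.2 | 47% |
| 75% | 232 | 38.7 | 44% |

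At N = 200, a site with 34 to 101 patients (17% to about 50% of the trial) meets the fraction but fails the count, and the count is about three times the fraction (101.5/33.3). If recruitment stopped well before the trigger, N is smaller and the gap wider: at N = 150 the fraction needs 26 patients, and 102 is 68% of the trial.

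**Outputs for ES40.** The addendum's contents list has no ES40-only or ES40-excluded table under 14.2.1 (oxygen withdrawal) or 14.2.2 (discharge). The addendum re-plots both endpoints, but by dose pair. Site location is a subgroup for the primary endpoint only; the discharge forest plot (Figure 14.2.2.2) has four subgroup factors, none of them site.

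**The case against.** The strongest reply is that the fraction is the rule. Section 7.6.4 states it twice, once for separate sites and once for pooled ones, and the count is only a parenthetical gloss. Under the pooling clause, a site with more than one sixth of the patients cannot go into Other Sites. The shells for the multivariate models and for the safety subgroup table name the site categories without any count. This stands. It means the plan does not clearly impose a cut of 101; it gives two instructions that conflict.

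A reader might go further and infer that the trial stopped near 200 patients, that no site short of half the trial can be separated, and that the site subgroup therefore vanishes. The documents do not support this. The figure of 200 depends on an assumed event share; 102 patients is less than half once N exceeds 204; and the subgroup vanishes only if the count is programmed and no site reaches 102.

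A reader might also infer that nothing planned shows the primary result without ES40. That too is more than the text allows. If the fraction governs and ES40 alone exceeds one sixth, the Other Sites row of the forest plot is the ES40-excluded hazard ratio for each dose. ES40's size is not given and the shell leaves two named-site slots, so this cannot be settled either way. It would help the primary endpoint only. The site covariate in the Cox models, if stepwise selection keeps it, gives a site main effect rather than a treatment effect without ES40.

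Finally, no passage says why ES40 was singled out. The addendum is explicitly post hoc and promises no leave-one-site-out analysis of the primary endpoint, so the absence of one is not an error.

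**Conclusion.** The point holds as an internal contradiction. The count of more than 101 is one sixth of 609, is wrong for the trial as it ended, and remains in four places. Over an assumed N of 174 to 232, the stated fraction corresponds to about 29 to 39 patients and the printed count to a site with about 59% to 44% of the trial. The consequence, pooling of sites that meet the rule, follows only if the count rather than the fraction is programmed. The actual N and the site sizes are not in the documents, so it cannot be said which sites are affected.

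The stratified log-rank test in the ITT population and its Hochberg adjustment are untouched. The gap in the ES40 tables is confirmed, but it is a reason for an optional addition, not a second defect.

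**What to change.** In SAP sections 7.6.4 and 7.7.7, in the version 4.0 shell for Figure 14.2.1.2 and in the addendum shell for Figure 14.2.1.2.1, delete the counts or replace them with: more than 1/6 of the patients actually randomised (N/6). The multivariate covariate should use the same definition. The fraction was already in the SAP before database lock, so the correction can be recorded as a clarification and is not a data-driven choice. It costs a wording change in four places and, if the count was programmed, a re-run of the outputs that use site location. No new data are needed.

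Optional, and labelled post hoc: repeat Tables 14.2.1.1.1 and 14.2.2.1.1 excluding Site ES40 and show the hazard ratios beside the full ITT results. This needs only a site filter on existing programs. The downside is two further post-hoc tables with less precise estimates.

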
*Programming notes (not part of the table):* 

- The displayed xxx do not reflect actual decimal precision. Please follow Section 2.11 for rounding rules.
- Omit those covariates with more than 10% of missing values from the multivariate analysis.
- Force to include the treatment arm in addition to the significant covariates.
- Remove the antiviral/immunomodulatory drug intake (no, yes), cumulative dose of corticoid therapy (≤60 mg, >60 mg) and total duration of corticoid therapy (<9 days, 9 to 11 days) variables from the modelling and the footnote.

The below tables are a repeat of table 14.2.4.1:

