#### 7.6.5 Exploratory Analysis

A multivariate analysis will be performed for the primary and key secondary efficacy endpoint, including the treatment group, randomisation stratification factors and all the above subgroup variables as covariates. Those covariates with more than 10% of missing values will be omitted from the multivariate analysis. A stepwise selection model will be used, with significant level equal to 0.2 and 0.05, to enter into the model and to remain in the model, respectively.Treatment group will be forced to be included in addition to the significant covariates.

Time-to sustained withdrawal of oxygen supplementation will be compared between each dose of plitidepsin versus control arm receiving the antiviral control arm, ie, the regulatory-approved antiviral for those patients randomised to the control arm (remdesivir or favipiravir).

Time-to sustained withdrawal of oxygen supplementation will be analysed using the Kaplan-Meier method and 25th percentile, median and 75th percentile time will be presented for the plitidepsin arms and control arm receiving the antiviral control

Sponsor Name: Pharma Mar S.A. Sponsor Protocol ID: APL-D-003-20

arm, together with 95% CIs. The 95% CIs will be computed based on Brookmeyer-Crowley method and using a log log transformation. The mean time to sustained withdrawal of oxygen supplementation and its standard error will be also presented for the pooled plitidepsin arms and control arm.

Time-to sustained withdrawal of oxygen supplementation between each dose of plitidepsin versus control arm receiving the antiviral control arm will be compared using a stratified log-rank test, including the randomisation stratification factors as covariates, ie, Geographical Region (Europe vs. Rest of the World), Charlson Comorbidity index (0-1 vs. >1) and pre-baseline Barthel index ( $\geq$ 90 versus <90) as derived using the eCRF data. The 2-sided p-values for the comparison of the pooled plitidepsin arms versus control arm will be presented.

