#### Statistical Analysis Plan

Sponsor Name: Pharma Mar S.A.	
Sponsor Protocol ID: APL-D-003-20	Labcorp Drug Development Study ID: 000000213894

- 15 Treatment-emergent adverse events (TEAEs): TEAEs should be documented and recorded at each visit (ie, from initiation of study treatment on Day 1 through at least Day 31), grading severity assessed using National Cancer Institute (NCI) Common Terminology for Adverse Events (CTCAE) v5.0, and relationship to study treatment assessed by investigator judgement
- 16 Concomitant medications: Concomitant medications and treatments will be recorded for all patients from 28 days before the start of study treatment and through study Day 31 (±3 days). All COVID-19 vaccinations should be recorded, regardless when they were given, until the end of study.
- 17 Dexamethasone treatment: On all study arms, patients will receive dexamethasone phosphate 8 mg/day IV (equivalent to 6.6 mg dexamethasone base) on Days 1 to 3 (administered as a premedication in plitidepsin arms), following by dexamethasone phosphate 7.2 mg (equivalent to 6 mg/day dexamethasone base) PO/IV from Day 4 and up to a total cumulative dose of 60 mg of dexamethasone base (as per physician judgement according to patient clinical condition and evolution). The study allows up to a total cumulative dose of 60 mg of dexamethasone base (calculation of the total dose will also include corticosteroids administered within 72 hours before the start of the study treatment and dexamethasone administered as premedication).
- 18 Plitidepsin treatment: Plitidepsin 1.5 or 2.5 mg intravenous (IV) infusion for 60 minutes will be administered on Days 1 to 3. A 30 (±5)-minute window is allowed for the plitidepsin administration between each day, and plitidepsin should not be given earlier than 23.5 hours on Days 2 and 3 of previous day plitidepsin administration. No other antiviral agents to be administered during Days 1 to 3.
- 19 Remdesivir treatment: Consistent with local treatment guidelines, patients randomised to the control arm may receive remdesivir 200 mg IV on Day 1 followed by 100 mg/day IV on Days 2 to 5.
- 20 Favipiravir treatment: Consistent with local treatment guidelines, patients randomised to the control arm may receive favipiravir 1600 mg BID PO on Day 1, followed by 600 mg BID PO daily for 2 to 5 days.

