[a] Parameter Estimate, Standard Error, p-value, and Hazard Ratio based on a Cox proportional-hazards regression model with treatment group, randomisation stratification factors, ie, geographical region (Europe, Rest of the World), Charlson Comorbidity Index (0 - 1, > 1) and pre-baseline Barthel index ( $\geq 90$  versus < 90) as derived using the eCRF data, and patients included before and after amendment (Protocol v.6 or before, Protocol v.7), sex (female, male), age at study entry (18 to 39, 40 to 64,  $\geq$  65 years), race (asian, black, white, other), ethnic group (Hispanic or Latino, Not Hispanic or Latino), site location (Site XXX, Site XXX, Other Sites), use of antiviral therapies or immunomodulatory drugs through the study (Yes, No), previous COVID-19 vaccination status (Fully vaccinated, Non-fully vaccinated), anti-SARS-CoV-2 IgG at Day 1 (Non-positive, Positive), pre-randomisation dexamethasone (Yes, No), total duration of corticoid therapy ( $\leq$  9 days, [9 - 11] days, > 11 days), total cumulative dose of corticoid therapy (dexamethasone or equivalent) ( $\leq$  60 mg, > 60 mg), SARS-CoV-2 viral load (log10 copies/mL) at Day 1 before study drug administration ( $\leq 4$ , [4 - 7], > 7), time between onset date of COVID-19 symptoms and initiation of study treatment ( $\leq 5$  days, 6 - 10 days, > 10 days), body mass index (kg/m2) at Screening (< 30,  $\geq$  30), hypertension at Screening (Yes, No), myocardial infarction (Yes, No), consective tissue disease (Yes, No), periptic ulcer disease (Yes, No), liver disease (Yes, No), cerebrovascular disease (Yes, No), dementia (Yes, No), thronic obstructive pulmonary disease (Yes, No), moderate or severe chronic kidney disease (Yes, No), solit tumor (None, Localized, Metastatic), leukemia (Yes, No), lymphoma (Yes, No), AIDS (Yes, No), ISARIC-4C mortality score (Low (0 - 3), Intermediate (4 - 8), High (9 - 14), Very high ( $\geq 15$ )), ISARIC-4C deterioration probability ( $\leq 25$ , (25 - 50], > 50), LDH at Baseline ( $\leq$  ULN, > ULN), creatinine at Baseline ( $\leq$  ULN, > ULN)

- The displayed xxx do not reflect actual decimal precision. Please follow Section 2.11 for rounding rules.
- Omit those covariates with more than 10% of missing values from the multivariate analysis.
- Force to include the treatment arm in addition to the significant covariates.

Variable	Parameter Estimate	Standard Error	p-value	Hazard Ratio

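### Subgroup and exploratory adjusted hazard ratios based on post-randomisation steroid, antiviral and immunomodulator use are not valid treatment effects; the addendum drops these variables only from its post-hoc repeats

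*SAP*

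**What the plan says.** SAP version 4.0, section 7.6.4, lists among the additional subgroups for the primary endpoint:

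- "Use of antiviral therapies or immunomodulatory drugs through the study: Yes or No"
- "Total duration of corticoid therapy", in bands of under 9, 9 to 11 and over 11 days
- "Total cumulative dose of corticoid therapy (dexamethasone or equivalent"), split at 60 mg

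Section 7.6.5 then builds a multivariate model for the primary and key secondary endpoints, "including the treatment group, randomisation stratification factors and all the above subgroup variables as covariates". Selection is automatic: "A stepwise selection model will be used, with significant level equal to 0.2 and 0.05" for entry and retention, with treatment forced in. The version 4.0 shells follow suit. The footnote of Table 14.2.4.1 includes "use of antiviral therapies or immunomodulatory drugs through the study (Yes, No") and both steroid variables, and Figure 14.2.1.2 gives all three their own rows. The shell of Table 14.2.4.2 shows no covariate list in the text at hand; its content follows from section 7.6.5.

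Appendix 4, note 17, says how steroid exposure arises. After Day 3, dexamethasone continues up to a cumulative total "as per physician judgement according to patient clinical condition and evolution".

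The SAP addendum (version 2.0, 12 September 2023) carries this programming note under Table 14.2.4.1.1: "Remove the antiviral/immunomodulatory drug intake (no, yes), cumulative dose of corticoid therapy" and steroid duration. The same instruction stands under Table 14.2.4.2.1 and Figure 14.2.1.2.1.

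**The concern.** A subgroup factor or covariate leaves the randomised comparison intact only if treatment cannot change it. These three do not meet that condition. In an open-label trial where steroid is continued according to how the patient is doing, a patient who comes off oxygen sooner will tend to stop steroid sooner. Steroid duration is then partly a record of the endpoint, and comparing arms within a duration band compares patients selected on their outcome. Cumulative dose follows duration.

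Antiviral and immunomodulator use has a further difficulty. Section 2.2 allows control patients an approved antiviral as part of study treatment, while Appendix 4, note 18, excludes other antivirals on Days 1 to 3 for plitidepsin patients. Section 7.6.4 does not say whether a control patient's study antiviral counts as *Yes*. If it does, *Yes* mixes Day 1 guideline choices in one arm with later treatment of patients doing badly in both.

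Section 6.2 treats later antiviral or immunomodulatory therapy as an intercurrent event and offers subgroup analyses in connection with its possible impact. A split on the event itself cannot show that impact. At stake are the interpretation of several forest-plot rows and of the only model in version 4.0 that adjusts beyond the stratification factors.

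**Working it through.** **1. The plan's own figures, and whether they depend on these variables.** Section 2.3 gives HR 1.4, one-sided alpha 0.0125, at least 80% power, 530 events over three arms and 353 per pair.

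- Fixed design: 4 × (2.241 + 0.842)² / (ln 1.4)² = 336 events.
- With 353 events: (ln 1.4 × √353)/2 − 2.241 = 0.919, power 82.1%. With the futility look at 116 events (rho 1.18), power is 80.0%.
- 353 × 1.5 = 529.5, i.e. 530.
- Smallest significant HR: exp(2 × 2.241/√353) = 1.269, stated as 1.27.

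The figures reproduce. They rest on the log-rank test of section 7.6.1, stratified by region, Charlson index and Barthel index. The supportive Cox model uses the same three factors. None of the variables at issue enters either analysis.

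**2. What the steroid bands capture.** Appendix 4, note 17, gives 6.6 mg of dexamethasone base per day on Days 1 to 3, then 6 mg per day up to a total of 60 mg.

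- First three days: 3 × 6.6 = 19.8 mg.
- Remainder: 60 − 19.8 = 40.2 mg, and 40.2/6 = 6.7 days.
- Total: 3 + 6.7 = 9.7 days without earlier steroid.

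The middle band is therefore roughly the full course, the lowest band mainly an earlier stop and the highest an extension. The bands sort patients partly by recovery.

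**3. Steroid duration: size of the bias.** Large-sample Cox simulation, 40,000 per arm, control median 8 days, follow-up 31 days. From the SAP: HR 1.4 and the 8-day median. Assumed, because the SAP gives no stopping data: steroid ends on average 2 days after oxygen withdrawal, with random spread (SD) of 1 to 8 days; severity spread on the log-hazard is 0 or 0.8.

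| True HR | Severity SD | Unadjusted HR | Adjusted for duration band |
|---|---|---|---|
| 1.4 | 0 | 1.37–1.39 | 1.18–1.27 |
| 1.4 | 0.8 | 1.26–1.28 | 1.11–1.18 |
| 1.0 | 0.8 | 1.00–1.01 | 1.00–1.01 |

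(With severity spread the unadjusted value already lies below 1.4, because severity is left out of the model. The comparison that matters is along each row.)

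With a true HR of 1.4 for every patient, the band-specific HRs were 1.06–1.14 (under 9 days), 1.01–1.15 (9 to 11) and 1.20–1.43 (over 11). The forest plot would show variation by steroid duration that is an artefact. In trial-sized simulations with steroid stopped 0 to 2 days after oxygen withdrawal, an unadjusted HR of 1.40–1.41 fell to 1.24–1.25, and duration band was significant at 0.05 in essentially every trial. Under these assumptions stepwise selection would keep it.

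Cumulative dose was not simulated separately. The argument there is that dose accrues with duration.

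**4. Antiviral or immunomodulator use: direction of the bias.** Same set-up, severity SD 0.8. Later use is given to patients still on oxygen after day 4, more often if severe. Early use unrelated to severity is added in one arm at an assumed rate.

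| Extra early use | True HR 1.4: unadjusted → adjusted | HR in *Yes* subgroup | True HR 1.0: adjusted |
|---|---|---|---|
| none | 1.28 → 1.30 | 1.26 | 1.00 |
| control 30% | 1.27 → 1.13 | 0.86 | 0.89 |
| control 60% | 1.27 → 1.01 | 0.73 | 0.80 |
| plitidepsin 20% | 1.26 → 1.39 | 1.68 | 1.08 |
| plitidepsin 40% | 1.26 → 1.48 | 1.95 | 1.16 |

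The plitidepsin rows would have to come from immunomodulators or from antivirals after Day 3, given note 18. They show that the direction depends on who receives these drugs, which the SAP does not settle.

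**5. Version 4.0 beside the addendum.** Version 4.0 (21 April 2023) contains the three variables. The addendum's deletion applies to Tables 14.2.4.1.1 and 14.2.4.2.1 and Figure 14.2.1.2.1, all labelled post hoc. Its introduction presents it as supplementing version 4.0, and it does not withdraw Figure 14.2.1.2 or Tables 14.2.4.1 and 14.2.4.2.

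**The case against.** The strongest reply is that nothing confirmatory depends on this. The three variables sit in subgroup rows and in an exploratory stepwise model; the subgroup Cox models themselves adjust only for the stratification factors; no alpha, decision rule or event count is involved. That stands, and it limits the weight of the point.

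A reader might infer that all three adjustments bias the effect towards none. The documents do not support that. Attenuation is the likely direction for steroid duration. For antiviral or immunomodulator use the result can move up, down or hardly at all.

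A reader might also infer that all three exposures are decided after randomisation by recovery. That is too wide. Section 2.2 counts steroid from the 72 hours before study treatment towards the 60 mg total, and a control-arm antiviral may be a Day 1 choice under local guidelines. *Wholly or partly* after randomisation is as far as the text goes.

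It can fairly be said that the sponsor has already recognised the problem. The addendum's notes remove the whole variables. Their failure to name the over-11-day band does not keep that band. By-arm description is already planned (addendum Table 14.3.1.1.1; version 4.0 Tables 14.1.4.3, 14.2.3.14 and 14.2.3.15). What the addendum does not do is withdraw the version 4.0 outputs, so the affected estimates keep pre-specified status while the versions without these variables are labelled post hoc.

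Finally, the database was locked on 26 April 2023. Removing pre-specified outputs after lock in an open-label trial is more than an edit of wording and has to be documented as a post-lock change.

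**Conclusion.** The point holds for the subgroup rows and for the exploratory adjusted model. Hazard ratios within, or adjusted for, steroid duration, cumulative steroid dose or antiviral/immunomodulator use cannot be read as treatment effects.

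For steroid duration, a true HR of 1.4 would probably appear as about 1.2 to 1.3 after adjustment, or lower where patients differ widely in severity. No bias appeared under a true HR of 1. For antiviral/immunomodulator use the direction is unknown, and an apparent effect can arise where there is none. These sizes rest on assumed links between drug use and recovery and on assumed rates of use, since the SAP gives neither.

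The primary log-rank test, the supportive Cox model, and the planned event count and power are unaffected. This should be corrected, but it does not threaten the primary result.

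**What to change.** Remove the three variables from the subgroup list in section 7.6.4 and from the covariate set in section 7.6.5, and therefore from Figure 14.2.1.2, Table 14.2.4.1 and Table 14.2.4.2. Keep pre-randomisation dexamethasone, which is a baseline factor.

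State, as a documented post-lock change, that addendum Tables 14.2.4.1.1 and 14.2.4.2.1 and Figure 14.2.1.2.1 supersede the corresponding version 4.0 outputs. If those outputs have already been produced, keep them and label the affected estimates as descriptive and not as treatment effects.

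The cost is a documented amendment or a labelling note, plus the loss of a few exploratory subgroup rows. The programming change has already been specified in the addendum.
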